**Nudging Primary Care Providers toward Guideline-Recommended
Opioid Prescribing through Easier and More Convenient EHR
Information Design**

R33 Clinical Trial
MPIs: [name] and [name]

NCT04295135

IRB #1911922583

Mar 5, 2024

CT. Gov: Statistical Analysis Plan

Study title: Nudging Primary Care Providers toward Guideline-Recommended Opioid Prescribing through Easier and More Convenient EHR Information Design

To assess the OneSheet effects on guideline-concordant care, we collected data from participating clinicians' visits with patients meeting several criteria described below. The criteria were: 1) 18+ years old; 2) no cancer diagnosis in the prior 3 years; 3) meet the following indications of chronic pain over the most recent 24 months:

- a. 3+ unique* instances of a qualifying pain diagnosis (either billed diagnosis or problem list) OR
- b. 3+ unique* prescriptions for one or more of the following drugs: an opioid ("opioid agonist," "opioid partial agonist," "opioid combinations"), Tramadol, Nortriptyline, Amitriptyline, Gabapentin, Pregabalin, Duloxetine, desipramine, milnacipran, tapentadol OR
- c. 2 unique* instances of a qualifying pain diagnosis AND 2+ unique* pain medication prescriptions containing one or more of the drugs listed in b.

*"unique", for Diagnoses and medications was defined as separated by at least 30 days from any previous qualifying diagnosis or prescription.

Because chronic pain treatment is often discussed during visits not explicitly identified as related to chronic pain, any visit that a qualifying patient has with a participating primary care clinician was considered as a qualifying visit for the trial. The data for qualifying visits was collected one year before OneSheet access was granted (October/November 2019) to May 2022 (18 months of the trial period).

Outcomes: We constructed six visit-level binary outcomes that could be measured with electronic health record (EHR) data and reflected recommendations in the 2016 CDC opioid prescribing guideline: 1) recording pain-related goals in the last 90 days; 2) recording pain and function via the Pain, Enjoyment, and General (PEG) assessment in the last 90 days; 3) checking the prescription drug monitoring program (PDMP) in the last 90 days; 4) assessing UDS results in the last calendar year; 5) ordering medications for opioid use disorder (MOUD) within seven days of the visit; and 6) ordering Naloxone within seven days of the visit.

Each outcome was set to 1 if the patient met the lookback criteria outlined above (e.g., 90 days for pain-related goals, PEG, and PDMP; 1 year for UDS, seven days for MOUD and Naloxone), or if the provider completed a given task one week following the visit (a 7-day grace period). For PDMP review, there was no one-week grace period because PDMP review is recommended by the CDC (and mandated by many states) to occur at the time of opioid prescribing.

The outcomes of pain-related pain and function goals and PEG assessments were evaluated for all patients with chronic pain, while the CDC recommendations for PDMP checking, UDS review, MOUD ordering, and Naloxone ordering only apply to patients on long-term opioid therapy (LTOT). We identified visits for patients on LTOT as those involving an opioid analgesic prescription lasting at least 28 days, per the Agency for Healthcare Research and Quality's CDS Connect recommendation for assessing opioid therapy (Agency for Healthcare Research and Quality, 2018).

As an example outcome, if a patient on LTOT had not had a UDS result in the last calendar year, but the provider ordered a UDS on the day of the visit, the outcome would be set to 1 (guideline-concordant). Similarly, if the patient had a UDS result in the last calendar year, the outcome would be set to 1 because at the time of the visit, the clinician was concordant with the CDC guideline recommendations for UDS review. If both a) a UDS had not been completed in the last year and b) the clinician did not order a UDS within one week of the visit, the outcome would be set to 0 (non-concordant).

Statistical Analysis: We used descriptive statistics to compare the demographic characteristics of clinicians assigned to the intervention group versus the control. We computed our outcomes at the patient-visit level for visits by qualifying patients with study providers for the 12 months before the OneSheet went live (the baseline period) and 18 months following OneSheet go-live. We excluded patients from the sample who had visits during the study period with both treatment and control clinicians to ensure that outcomes were not compared across trial arms for the same patient. To estimate the effect of OneSheet on our outcomes, we used a multi-level linear probability model including patient demographics, clinician random effects, and indicator variables for a) site; b) treatment and control clinicians; and c) pre-/post-OneSheet go-live. We included an interaction term for treatment and post-OneSheet go-live, the coefficient for which estimates the causal effect of OneSheet on our outcomes of interest. Statistical tests were 2-tailed, and p-values < 0.05 were considered statistically significant. Data analyses were performed from November 2022 to September 2023 using *tidyverse*, *lubridate*, *fixest*, and *lme4* R packages in RStudio (Bates et al., 2015; Berge, 2018; Grolemund et al., 2011; Wickman, 2017).

References:

Agency for Healthcare Research and Quality, 2018. Recommendation 7: Opioid therapy risk assessment. Retrieved March 1, 2024, from
<https://cds.ahrq.gov/cdsconnect/artifact/recommendation-7-opioid-therapy-risk-assessment>

Wickham H. The tidyverse. R package ver 1 1 1 [Internet]. 2017; Available from:
https://slides.nyhackr.org/presentations/The-Tidyverse_Hadley-Wickham.pdf

<https://www.jstatsoft.org/v40/i03/>

Bergé L (2018). “Efficient estimation of maximum likelihood models with multiple fixed-effects: the R package FENmlm.” CREA Discussion Papers.

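### MOUD, scored at every long-term opioid visit, is an order rate and not a measure of guideline concordance; for naloxone only the seven-day window is open

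*SAP*

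**What the plan says.** The SAP states its purpose in its opening words: "To assess the OneSheet effects on guideline-concordant care". The Outcomes section lists six visit-level outcomes said to reflect the 2016 CDC guideline. Two of them are "ordering medications for opioid use disorder (MOUD) within seven days of the visit" and "ordering Naloxone within seven days of the visit".

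One scoring rule covers all six. Goals, PEG and PDMP look back 90 days; the remaining lookbacks are "1 year for UDS, seven days for MOUD and Naloxone". A task completed in the week after the visit also counts, except for PDMP.

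Goals and PEG are scored for all chronic pain patients. PDMP, UDS, MOUD and naloxone are scored only for patients on LTOT, whose visits are "those involving an opioid analgesic prescription lasting at least 28 days". Nothing is said about opioid use disorder beyond spelling out the abbreviation MOUD.

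The UDS example shows how scores are meant to be read. A result from the past year scores 1, as concordant at the visit. No result and no timely order scores 0, labelled non-concordant.

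The protocol's purpose statement (section B) has two aims: the effect on ordering and related behavior, and whether decisions become more concordant with the guideline. Under Statistical Analysis, the treatment-by-post interaction in a linear probability model is taken as the causal effect on each outcome.

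**The concern.** A concordance score should be 1 when the recommended care is in place or is supplied, and 0 when it is indicated and missing. The MOUD rule does not do this, for two reasons:

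- **No disorder required.** By its name the treatment is for opioid use disorder, yet the denominator is every LTOT visit. A patient without the disorder scores 0 at each visit unless MOUD is ordered.
- **Little credit for continuing treatment.** A patient already on MOUD scores 0 when no order falls within a week either side of the visit.

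Under the SAP's stated aim, a low MOUD rate could be reported as low concordance, and a small or null coefficient as no gain in it. The measure supports neither statement. A positive coefficient shows more ordering. It shows better concordance only if the added orders went to patients with the disorder who lacked treatment, which the data as scored do not reveal.

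Naloxone shares the seven-day lookback, so a patient with an older order also scores 0. Whether that 0 is a shortfall depends on how long an order is meant to count, which the documents do not say.

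**Working it through.** The documents give no power calculation, effect size, event rate, share of patients with the disorder or visit frequency for these outcomes, so there is no figure to reproduce. The first step follows from the SAP's scoring rule. The others illustrate size on assumed inputs.

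**1. Span in which an action earns credit (SAP, Outcomes)**

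| Outcome | Back + forward (days) | Span | Scored on |
|---|---|---|---|
| Goals, PEG | 90 + 7 | 97 | all chronic pain visits |
| PDMP | 90 + 0 | 90 | LTOT visits |
| UDS | 365 + 7 | 372 | LTOT visits |
| MOUD, naloxone | 7 + 7 | 14 | LTOT visits |

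**2. MOUD: effect of the denominator**

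Let *p* be the share of LTOT visits made by patients with the disorder, and *r* the chance of an order within the 14-day span at such a visit. If MOUD is ordered for no one else, the observed rate is *p* × *r*. Its ceiling (*r* = 1) is *p*, and a change Δ in *r* appears as *p* × Δ. Take *p* from 5% to 30% (assumed) and Δ = 30 points:

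- *p* = 0.05: ceiling 5%; 0.05 × 30 = 1.5 points.
- *p* = 0.10: ceiling 10%; 0.10 × 30 = 3.0 points.
- *p* = 0.30: ceiling 30%; 0.30 × 30 = 9.0 points.

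The same behavior change thus spans a factor of 9.0 / 1.5 = 6. This trial has one value of *p*, but it is not reported, so a reader cannot undo the scaling. Patients on continuing MOUD without a nearby order lower *r* further.

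**3. Naloxone: effect of the window**

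Assume one order per patient, placed with equal chance at any of *k* evenly spaced visits over 18 months (548 days), and a 20-point difference between arms in the share of patients ever given an order. The visit-level difference is 20 × (mean visits credited) / *k*. Under the seven-day rule one visit is credited.

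- *k* = 3 (183 days apart): 20/3 = 6.7 under either rule.
- *k* = 6 (91 days apart): 20/6 = 3.3 under either rule. This sits on the edge: at exactly 90 days apart the 90-day rule credits (5 × 2 + 1)/6 = 1.83 visits, giving 6.1.
- *k* = 10 (55 days apart): 2.0 under seven days; the 90-day rule credits (9 × 2 + 1)/10 = 1.9 visits, giving 3.8.
- *k* = 19 (28 days apart): 20/19 = 1.05 under seven days; the 90-day rule credits (16 × 4 + 3 + 2 + 1)/19 = 3.68 visits, giving 3.88.

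The window may matter not at all or a great deal. Only the trial's visit pattern can tell.

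**4. What a longer window would cost**

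With visits spread evenly over the 548 days, a 90-day lookback reaches before go-live for 90/548 = 16% of post-period visits, and a one-year lookback for 12/18 = 67%.

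**The case against.** Both outcomes are named as ordering outcomes, and the protocol's first aim is ordering behavior. As visit-linked order rates they are legitimate, and their arm contrast is usable. A short window also has merit in this design: it ties the order to the visit and limits credit for orders placed before go-live, which OneSheet could not have influenced. All of this stands. None of it turns the MOUD rate into concordance.

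A reader might infer several stronger conclusions that the documents do not support:

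- **That naloxone has the same defect as MOUD.** The SAP states that the naloxone recommendation applies to LTOT patients, so the denominator matches. Whether an order more than seven days old satisfies the recommendation rests on the guideline, which the documents do not reproduce. A flat ban on concordance conclusions for naloxone would go too far.
- **That the seven-day lookback alone was left unexplained.** The SAP gives no separate reason for the length of any lookback. The sentence "For PDMP review, there was no one-week grace period because PDMP review is recommended by the CDC" explains a missing grace period, not a lookback. The contrast with the other four outcomes shows a difference, not in itself an error.
- **That the SAP calls a MOUD score of 0 non-concordant.** That label is written out only for UDS. Extending it to MOUD is an inference from the shared rule and the stated aim.
- **That the plan ranks coefficients across outcomes, or reports low MOUD concordance.** It does neither. The harm depends on how results are worded.

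**Conclusion.** For MOUD the point holds on the SAP's text alone. The outcome is presented under a concordance aim, but the rule measures orders within a week of an LTOT visit, whatever the patient's disorder status. Its level and its treatment-by-post coefficient are scaled by an unreported share. Neither the level nor a small or null coefficient can be read as concordance or as lack of gain in it.

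For naloxone the point is conditional. It is safest read as an order rate until the sponsor shows that an order older than seven days does not satisfy the recommendation.

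It would be wrong to infer that the treatment-by-post coefficient is shown to be biased for the order rate. One caution applies: LTOT status rests on a prescription that OneSheet may itself change, so the set of LTOT visits could differ by arm. The documents do not show whether it does.

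The sizes (1.5–9.0 points for MOUD; none to 1.05 against 3.88 points for naloxone) rest on assumed disorder shares, order patterns and visit spacing, and are not estimates for this trial.

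**What to change.** 1. **MOUD.** Report and interpret it as an order rate within seven days of an LTOT visit, with base rates by arm and period, and draw no concordance conclusion from it. If the diagnosis is available under the approvals, also give the share of LTOT visits by patients with the disorder, and an analysis among patients with it recorded before go-live. The protocol's list of data elements (section K-HIPAA) names chronic pain diagnosis but not opioid use disorder, so availability must be checked.
2. **Naloxone.** Report it as an order rate unless the sponsor shows that an order older than seven days does not satisfy the recommendation. State the reason for the seven-day window.
3. **Optional, labelled post hoc.** Rescore naloxone with a 90-day lookback plus the seven-day grace period, in the same model. Read it only as showing whether the result depends on the window; it cannot settle concordance. State that about 16% of post-period visits would look back before go-live if visits are spread evenly.
4. **LTOT.** Note that the LTOT visit set could differ by arm.

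Items 1, 2 and 4 cost wording and one table, plus the MOUD subgroup analysis if the diagnosis can be used. For item 3, medication orders are a listed data element, and eligibility already requires patients to "meet the following indications of chronic pain over the most recent 24 months", partly through prescriptions. Earlier orders are therefore likely to be reachable, though the SAP does not show that naloxone orders were extracted that far back. If they were not, drop the first 90 baseline days in both arms and rerun the seven-day rule on the same visits. That removes 90/365 = 25% of baseline visits, leaving about 9.04 of 12 months. The standard error then grows by a factor of √[(1/9.04 + 1/18)/(1/12 + 1/18)] = 1.09.

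The analyses ended in September 2023, so added analyses cannot replace the main result. The downside is a narrower claim and a little more analysis.

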The Chronic Pain OneSheet (OneSheet) is a dashboard that was developed at Eskenazi, and built in Epic at Eskenazi Health and at Wake Forest Baptist Health, in close collaboration with the Primary Care leadership and clinics at both institutions. The Dashboard does not provide new information to providers, but rather works by aggregating and structuring information that is already being collected, and that is available in other places in the medical record. By aggregating and structuring this information in a more convenient manner, the goal of the OneSheet is to make the information that is important in clinical decision-making more readily available, and to reduce the amount of time that providers need to spend locating this information.

The purpose of the study is to determine whether and how having access to the Chronic Pain OneSheet activity in Epic affects the ordering, prescribing, goal-setting, risk monitoring, and outcome measuring behavior of participating providers in visits with patients with chronic pain. We will also assess whether access to the Chronic Pain OneSheet results in primary care providers making chronic pain treatment decisions that are more concordant with the CDC Guideline for Prescribing Opioids for Chronic Pain.

q22123

List and describe all research interactions and/or interventions, including the frequency and duration of procedures, and length of participation for individual subjects.

The Chronic Pain OneSheet (OneSheet) is a dashboard that was developed and built in Epic at Eskenazi Health, in close collaboration with the Eskenazi Health Clinical Information Technology Governance committee, and Eskenazi Health Primary Care leadership and clinics. It was subsequently built into Epic at Wake Forest Baptist Health primary care clinics, in close collaboration with WFBH Primary Care leadership. The Dashboard does not provide new information to providers, but rather works by aggregating and structuring information that is already being collected, and that is available in other places in the medical record. By aggregating and structuring this information in a more convenient manner, the goal of the OneSheet is to make the information that is important in clinical decision making more readily available, and to reduce the amount of time that providers need to spend locating this

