Please describe the plan for management and communication of IRB-related information to sites and/or non-affiliated investigators, including ensuring that non-affiliated investigators are familiar with and will follow IU HRPP policies and procedures, that required reporting and requests for amendments by non-affiliated investigators are submitted to the IU IRB, and that IRB decisions and approved documents are communicated. Alternatively, attach a document describing this plan.

The lead investigator and the site-specific PI for the study at Indiana University will be responsible for ensuring that all non-affiliated investigators complete all training and tasks required by IU HRPP policies, and follow the protocol that is approved by the IU IRB. All study personnel will meet regularly to communicate any decisions by the IRB, and to ensure that all policies and procedures are being followed at all sites. All IRB approved, and stamped documents will be circulated to study personnel.

q710a

Is this a multi-center study or multi-site clinical trial?

Yes

q711a

State the number of subjects to be enrolled in the study at all sites.

250

q712a

Is the Lead investigator at IU?

Yes

q714

Describe the plan for the management and communication of multi-site information that may be relevant to the protection of participants.

The study teams at all sites have a standing biweekly meeting to manage the study and communicate information between sites. Data Use Agreements between the sites will protect the sharing of participant information among the study team. Files with participant information will be shared between the sites only when necessary and then only via secure electronic shared drives.

D-Recruitment Methods

q23236

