The members of the study team conducting the analysis will access the limited dataset through a secure network drive, specifically created for that purpose. Only the members of the study team who are involved with the analysis will be granted access to the secure folder. Furthermore, all information collected will be stored in locked filing cabinets or password protected secure network drives on encrypted devices. Data will continue to be protected on secure network drives throughout the analysis and accessed only by members of the research team. All study dissemination activities, such as presentations and journal articles, will report data in the aggregate and not identify individuals.

q23655

Explain how the research could not be practicably conducted without waiver of authorization or alteration of authorization requirements.

The research is concerned with the clinical behaviors of primary care providers when they are treating patients with chronic pain and using their EHR in daily practice. Because primary care providers see many patients with chronic pain on a daily basis, it would be impractical for researchers or clinic staff collaborators to intervene in each of these visits to obtain HIPAA authorization.

q23656

Explain how the research could not be practicably conducted without access to and use of identifiable PHI.

Regenstrief Data Core will require MRNs and dates of qualifying visits to create the limited dataset that will be shared with the study team. The limited dataset will include dates of

healthcare services provided. The limited dataset is required to complete our analysis determining if access to the OneSheet changes clinician behavior regarding pain medication prescriptions, treatment referrals, the setting of pain and function goals, and the assessment of opioid related risks (PDMP checks, urine drug screens, and PEG scores). Specifically, dates are required to analyze the effect of the OneSheet over time, and to measure guideline-concordance of clinician behavior (e.g., was the PDMP checked within the time span required by guidelines).

IRB Amendments

Approval date	Summary of changes
7/8/20	Added WF as a site, [name] named PI, [name] as site specific PI, Limited dataset instead of deidentified, updated recruitment process, added demographic survey, ICF edited, e-Consent added - a003
7/29/20	Updated recruitment talking points - a004

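### PDMP, UDS, MOUD and naloxone are analysed in a visit set that OneSheet itself may alter after go-live, and the SAP calls the coefficient causal with no selection caveat or check

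*SAP*

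**What the plan says.** The SAP's outcome section defines six visit-level binary outcomes. Pain-related goals and PEG are assessed in all qualifying chronic-pain patients. The other four are confined to LTOT because, in the SAP's words, the CDC recommendations on PDMP, UDS, MOUD and "Naloxone ordering only apply to patients on long-term opioid therapy (LTOT"). The operational rule is: "We identified visits for patients on LTOT as those involving an opioid analgesic prescription lasting at least 28 days". It gives no reference date, and it does not say whether the prescription must be written at the visit or already active then.

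Under Statistical Analysis, outcomes are computed for visits in the "12 months before the OneSheet went live (the baseline period) and 18 months following OneSheet go-live". The model is a "multi-level linear probability model including patient demographics, clinician random effects, and indicator variables for a) site", with further indicators for arm and period and their interaction. The SAP states that the interaction coefficient gives the causal effect of OneSheet on the outcomes. The only between-arm comparison it describes is of clinician demographics.

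The protocol's lay summary says the study asks whether and how OneSheet "affects the ordering, prescribing, goal-setting, risk monitoring, and outcome measuring behavior of participating providers in visits with patients with chronic pain". Its HIPAA section (q23656) says the limited dataset is needed for "determining if access to the OneSheet changes clinician behavior regarding pain medication prescriptions", among other behaviours.

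**The concern.** Randomising clinicians protects comparisons over all their visits. It does not by itself protect a subset that is chosen after randomisation by a variable treatment may affect. Here that variable is an opioid prescription of at least 28 days, and the trial's own documents name prescribing as a possible target of the intervention. If OneSheet led some clinicians to stop or shorten prescriptions, or to start them, the treatment arm's LTOT visits after go-live would be a different mix from those before.

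The interaction term removes stable arm differences, but not an arm-specific change in who is flagged. The clinician random effect and patient demographics do not remove it either, and the listed covariates include no opioid history and no patient effect. Excluding patients seen in both arms addresses a different problem. For these four outcomes the coefficient could therefore move through case mix with no change in concordance behaviour, and nothing in the plan would reveal it.

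**Working it through.** **What the documents supply.** They give the selection rule, the visit window, the model terms and an enrolment figure of 250 providers (Protocol, q711a). They give no outcome rates, no LTOT share, no visit counts and no power calculation, so there is no stated figure to reproduce. Every rate below is an assumption.

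**1. Exits only.** Let p be concordance among LTOT visits, s the fraction of the treatment arm's post-go-live LTOT visits that leave the set, and q the concordance of those visits. With no behavioural effect, the false effect is s(p - q)/(1 - s).

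| p | s | q | False effect (points) |
|---|---|---|---|
| 0.68 | 0.10 | 0.40 | 0.10 × 0.28 / 0.90 = +3.1 |
| 0.68 | 0.10 | 0.68 | 0 |
| 0.68 | 0.10 | 0.80 | 0.10 × (-0.12) / 0.90 = -1.3 |
| 0.68 | 0.05 | 0.40 | 0.05 × 0.28 / 0.95 = +1.5 |
| 0.68 | 0.15 | 0.40 | 0.15 × 0.28 / 0.85 = +4.9 |
| 0.05 | 0.10 | 0 | 0.10 × 0.05 / 0.90 = +0.6 |
| 0.05 | 0.10 | 0.20 | 0.10 × (-0.15) / 0.90 = -1.7 |

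The second row shows that a shift alone is not enough: the visits that move must also differ in concordance. The last two rows stand for a low-rate outcome, as MOUD or naloxone might be.

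**2. Does the model absorb it?** A simulated linear mixed model (arm by period, clinician random intercept) was fitted with no true effect. It used 100 clinicians, 40 visits before and 60 after go-live, two equal strata at 80% and 40%, and 20% of the lower stratum leaving in the treatment arm after go-live. That is s = 0.10, p = 0.60, q = 0.40, for which the formula gives 0.10 × 0.20 / 0.90 = +2.2 points. The mean coefficient over 60 runs was +2.1 points, and about 23% of runs had p < 0.05. The clinician effect and the arm and period terms leave the shift in place.

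**3. Offsetting moves.** If 10% leave at 40% and as many enter at 80%, concordance becomes 0.68 - 0.10 × 0.40 + 0.10 × 0.80 = 0.72. The false effect is +4.0 points although the flagged share has not changed.

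**4. What a baseline cohort would show.** Suppose patients with a qualifying prescription before go-live are followed whatever happens to their prescription, and visits after stopping score 0. With 10% extra stopping in the treatment arm, the estimate moves by -s × q: -4.0 points at q = 0.40, -6.8 at q = 0.68 and -8.0 at q = 0.80. If half of the concordant visits still score 1, these halve. At q = p = 0.68 the LTOT-visit analysis has no artefact, yet the cohort differs from it by 6.8 points (3.4 if half are kept).

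**5. Precision of a check on the flag.** Assume the 250 split into 125 clinicians per arm, a flagged share L = 0.20, V = 50 to 200 qualifying visits per clinician and period, and a clinician-by-period SD of 0.05 to 0.02. Then SE = sqrt(4 × (L(1 - L)/V + SD²)/125).
- V = 200, SD = 0.02: sqrt(4 × 0.0012/125) = 0.0062, so the 95% half-width is 1.96 × 0.0062 = 1.2 points.
- V = 50, SD = 0.05: sqrt(4 × 0.0057/125) = 0.0135, so the half-width is 1.96 × 0.0135 = 2.6 points.

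Losing 10% of a 20% flagged share is a 2-point fall. Power to detect it runs from 32% to 90%; for a 1-point fall it is 11% to 36%.

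**The case against.** The restriction is clinically sensible. The SAP says the four recommendations apply only to LTOT patients, so scoring other visits would measure something else. It also confines these outcomes to LTOT visits by definition, so its causal statement is not unlimited in population. Both points stand; what is missing is a caveat about selection.

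The mechanism is inferred. The protocol speaks of prescribing in general, and its listed prescribing data point is daily MMEs, which is a dose. A change in dose need not cross a 28-day duration threshold. If *involving* means already active at the visit, first visits after go-live are largely protected, although later ones are not. The meaning may lie in the AHRQ source the SAP cites, which is not available here. For a low-rate outcome the illustrated artefact is only -1.7 to +0.6 points. All of this limits the strength of the point without removing it.

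A reader might infer that the four results are biased. The documents do not support that: they show neither a shift by arm nor a concordance difference in visits that moved.

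A reader might also take a gap between the LTOT-visit analysis and a baseline cohort as proof of selection. Step 4 shows why that fails: a 6.8-point gap can arise with no artefact at all. An automatic rule built on the flag test plus four gap tests, each at 95%, would also trigger falsely in up to 1 - 0.95^5 = 23% of cases if the tests were independent.

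**Conclusion.** The concern holds as an unaddressed risk of bias in four of six outcomes. The analysed set has no anchor before go-live, the protocol treats its defining variable as open to influence by treatment, the model would not remove a differential shift, and the causal wording carries no caveat or check. Size and sign cannot be derived from the documents; the illustrations run from -1.7 to +4.9 points on assumed rates and include zero. Goals and PEG are not subject to the LTOT filter, although one route into the qualifying set ("3+ unique* prescriptions for one or more of the following drugs: an opioid" and other listed drugs) also counts prescriptions, over 24 months. This should be fixed; confidence is medium because no shift has been shown.

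**What to change.** Keep the LTOT-visit analysis, and state whether *involving* means written at the visit or active then. The SAP says analyses ran from November 2022 to September 2023, so label the following as post hoc.

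1. Fit the same treatment-by-period model to the indicator that a visit is flagged LTOT, among all qualifying visits. Report the interaction with its 95% CI, and the flagged shares and qualifying-visit counts by arm and period. Use the interaction, since a stable arm imbalance in flagged share does not bias the main estimate. A null result is not proof: entries and exits can offset (step 3), and precision for small shifts is limited (step 5).
2. As a descriptive sensitivity analysis only, repeat the four models in patients with an opioid analgesic prescription of at least 28 days in the 12-month baseline period. Report by arm the share of their post-go-live visits with no such prescription. Note that this cohort omits later LTOT starters and may score patients who stop opioids as non-concordant on tasks that no longer apply. It can therefore differ from the main analysis by several points without selection bias.
3. Describe the four coefficients as effects on concordance among LTOT-flagged visits, causal only if OneSheet did not change which visits are flagged. Present items 1 and 2 beside them, with no automatic relabelling rule.

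The cost is one extra model, four re-runs on data already extracted, and a more qualified causal statement.
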